2.14 Final analysis

Due to the early termination of study CQGE031C2302E1, a final analysis of all data collected up to last study visit will be performed when all subjects have completed the last study visit. Scope of the final analysis is described and summarized in Table 2-16. The outputs shell will be provided in CSR outputs TFL shells.

2.14.1 Final analysis sets

The enrolled set (ENR), the full analysis set (FAS), and the safety analysis set (SAF) as defined in Section 2.2, will be used for this final analysis. The following subpopulations will be considered in the safety and efficacy analyses for this final analysis:

- **Ligelizumab retreatment subpopulation** (as defined in Section 2.2.2): subjects in SAF who are treated with same dosage of ligelizumab in the extension study as in the core studies (C2302 and C2303).
- **Ligelizumab responder retreatment subpopulation** (as defined in Section 2.2.2): subjects in SAF who are treated with same dosage of ligelizumab in the extension study as in the core studies (C2302 and C2303) and achieved $UAS7 \leq 6$ at week 12 in the core studies.

- **Long term treatment subpopulation** (as defined in Section 2.2.2): subjects in SAF who receive ligelizumab treatment in the second half of treatment period without entering the second observation period. Due to study early termination, the definition of “continuous long term treatment subpopulation” will not be used for the final analysis.
- **Long term treatment with a rest subpopulation** (as defined in Section 2.2.2): subjects in SAF who received one-year ligelizumab treatment and moved to the second observation period before moving to the second half of the treatment period.
- **Self-administration subpopulation** (as defined in Section 2.13.2.1): subjects who have at least one injection with PFS administered by the participant herself/himself or a caregiver either in clinic or outside of clinic.

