2.1.1.2 Study periods

The following study periods will be considered for analysis:

- Screening period (SCR): from the date of signing informed consent form (ICF) to, and not include the date of the first ligelizumab treatment (i.e. V201) in extension, or the first visit in the first observation period (i.e. V101), whichever comes first.
- First observation period (OBS1): from Visit 101 up to Visit 199. The duration of OBS1 period for each subject varies, as it depends on occurrence of relapse ($UAS7 \geq 16$). Maximum duration of OBS1 is 36 weeks.
- First 12 weeks of the first half of the treatment period (TRT1A): from Visit 201 to Visit 204.
- Week 12 to Week 52 of the first half of the treatment period (TRT1B): from Visit 204 to Visit 214 or 301, whichever comes first.
- Entire first half treatment period (TRT1): from Visit 201 to Visit 214 or 301, whichever comes first.
- Second observation period (OBS2): from Visit 301 up to Visit 399. The duration of OBS2 period for each subject varies, as it depends on occurrence of relapse ($UAS7 \geq 16$). Maximum duration of OBS2 is 52 weeks.
- Second half of the treatment period (TRT2): Visit 214 to Visit 9998 (excluding Visit 301 to Visit 399)
- Follow-up period:
 - Subjects who do not complete a continuous 104-week treatment will enter the follow-up period (FU12) for 12 weeks duration and will only perform Visit 9999.
 - Subjects who have completed the full 104-week treatment period without interruption will enter the follow-up period (FU52) of 52 weeks duration and will perform Visit 501 to Visit 9999 (Week 116 to Week 156).

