2.6 Analysis of the key secondary objective

For retreatment efficacy evaluation (based on subjects who roll-over from C2302/C2303 and in the retreatment subpopulation):

- To describe the efficacy of ligelizumab 72 mg or 120 mg q4w in achieving complete control of chronic spontaneous urticaria (CSU) at Week 12 when used as retreatment
- To describe the efficacy of ligelizumab with respect to a reduction from extension study baseline in the UAS7 and its components (weekly itch severity score (ISS7) and weekly hives severity score (HSS7) at Week 12

- To describe the efficacy of ligelizumab in achieving an angioedema-free period at Week 12
- To describe the efficacy of ligelizumab in achieving Dermatology Life Quality Index (DLQI) = 0-1 at Week 12 when used as re-treatment

For self-administration efficacy evaluation (based on subjects who roll-over from all preceding studies and in the self-administration subpopulation):

- To describe the efficacy of ligelizumab in the treatment of CSU, 12 weeks after starting out-of-clinic self-administration

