2.6.1 Key secondary endpoints

For all secondary efficacy analyses, the FAS (or subpopulations within FAS) will be used. All listings and tables will be presented by treatment group unless stated otherwise. All data will be included in the analysis regardless of rescue medication use.

All secondary analyses to be performed in this study are described and summarized in

Table 2-9.

Table 2-9 Overview of analyses on secondary efficacy endpoints

Analysis Population and Analysis Period/time point	Endpoints and Analysis
Objective: to assess the retreatment efficacy of ligelizumab	

population: Ligelizumab retreatment subpopulation
 
period/time point: TRT1A/Visit204 (Week 12)
	
 • The proportion of subjects with completely controlled urticaria (UAS7 = 0) at Week 12 • Absolute change from extension study baseline in the UAS7 and its components (ISS7 and HSS7) at Week 12 • Cumulative number of weeks that subjects achieve weekly angioedema activity score (AAS7) = 0 between extension study baseline and Week 12 • Percentage of subjects achieving DLQI = 0-1 at Week 12
Objective: to assess the self-administration efficacy	

Population: self-administer subpopulation, who have at least one self-administration in TRT1B
 
Period/time point: 12 weeks after starting outside-clinic self-administration in TRT1B
	
 • The proportion of subjects with well-controlled disease (UAS7 ≤ 6), 12 weeks after starting self-administration

- Percentage of subjects achieving UAS7 = 0 (complete control of urticaria) at week 12 after retreatment of ligelizumab for subjects receiving the same dose regimen as in the core studies.

The proportion of subjects with UAS7 = 0 at Week 12 will be summarized in a descriptive manner, it will be provided together with 95% Clopper-Pearson exact confidence interval.

Similar missing data imputation rules as the primary endpoint analysis will be applied in this secondary efficacy endpoint analysis. The missing data imputation will be based on the proportion of subject with UAS7 = 0 at week 12.

- Absolute change from extension study baseline in UAS7 at Week 12 after retreatment of ligelizumab for subjects receiving the same dose regimen as in the core studies.

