2.13.2.1 Interim analysis set(s)

The Safety analysis set (SAF), as defined in Section 2.2, including all subjects who received at least one dose of study treatment will be used for all the analyses of this interim analysis.

Three types of administration defined in Table 2-13 are of interest in this interim analysis. The following subpopulations according to those types of administration will be considered in the safety and efficacy analyses for this interim analysis:

- **Outside-of-clinic self-administration:** participants who have at least one outside-of-clinic injection with PFS administered by either the participant herself/himself or a caregiver.
- **Self-administration:** participants who have at least one injection with PFS administered by the participant herself/himself or a caregiver either in clinic or outside of clinic.
- **In-clinic staff-administration:** participants who have all injections with PFS administered in clinic and by the site staff.

Definition of the above three subpopulations only depends on data in the first half of the treatment period. For example, participants who have all injections done in-clinic and by site staff in the first half of the treatment period, and start self-administration in the second half of the treatment period would belong to the in-clinic staff-administration subpopulation for the purpose of this interim analysis.

Table 2-13 Definition of type of administration

Type of administration	Definition
Outside-of-clinic self-administration	Outside-of-clinic injections with PFS administered by either the participant herself/himself or a caregiver
Self-administration	Injections with PFS administered by the participant herself/himself or a caregiver either in clinic or outside of clinic

In-clinic staff-administration	Injections with PFS administered in clinic and by the site staff
--------------------------------	--

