2.14.4 Efficacy analyses at final analysis

Primary and some of the key secondary endpoints will be analyzed at the final analysis, as described in Section 2.5 and Section 2.6. [REDACTED]

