2.14.8 Handling of missing values/censoring/discontinuations

The missing data handling and imputation rules as described in Section 2.5.3 and Section 2.6.3 will be applied on the primary and some key secondary endpoints, respectively. All the other analyses in the final analysis will be based on the observed data.

Table 2-16 Overview of final analysis

Population/ Analysis /Study Period	Endpoints
First treatment period (TRT1)	
Analysis: Efficacy Populations: 1) FAS 2) Ligelizumab retreatment subpopulation 3) Ligelizumab responder retreatment subpopulation Period/time point: TRT1/up to week 52	
• Proportion of subjects with well-controlled urticaria ($UAS7 \leq 6$) at Week 12

Analysis: Efficacy
 
Populations:
 
 1) FAS 2) Ligelizumab retreatment subpopulation 
Period/time point: TRT1/up to week 52
	
 • Proportion of subjects with completely controlled disease (UAS7 = 0) at Week 12

Analysis: Efficacy
 
Populations:
 
 1) FAS 2) Ligelizumab retreatment subpopulation 
Period/time point: TRT1/up to week 52
	
 • Absolute and percent change from extension study baseline in the UAS7 and its components (ISS7 and HSS7) at Week 12 • Percentage of subjects achieving DLQI = 0-1 at Week 12

Analysis: Efficacy
 
Populations:
 
 1) FAS 2) Ligelizumab retreatment subpopulation 
Period/time point: TRT1A/up to week 12
	
 • Cumulative number of weeks that subjects achieve weekly angioedema activity score (AAS7) = 0 between extension study baseline and Week 12

Analysis: Efficacy
 
Population: Self-administration subpopulation
 
Period/time point: 12 weeks after starting self-administration in TRT1
	
 • The proportion of subjects with well-controlled disease (UAS7 ≤ 6), 12 weeks after starting self-administration

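### The final self-administration endpoint has two populations and two possible starting points, which put the UAS7 assessment at Week 36 or at Week 24

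*SAP*

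**What the plan says.** **The rule in SAP 2.6.** The objective is efficacy "12 weeks after starting out-of-clinic self-administration". Table 2-9 (SAP 2.6.1) sets the time point as "12 weeks after starting outside-clinic self-administration in TRT1B". Its population is the "self-administer subpopulation, who have at least one self-administration in TRT1B", with no setting given. SAP 2.2.2 defines only one self-administration set, which requires at least one dose outside the clinic.

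**The rule for the final analysis.** SAP 2.14.4 states: "Primary and some of the key secondary endpoints will be analyzed at the final analysis, as described in Section 2.5 and Section 2.6". SAP 2.14.1, however, takes its self-administration set from the unplanned interim analysis: "subjects who have at least one injection with PFS administered by the participant herself/himself or a caregiver either in clinic or outside of clinic". Table 2-16 pairs that set with the time point "12 weeks after starting self-administration in TRT1". The setting is gone, and TRT1B has become TRT1. The interim section treats the two sets as different. Table 2-13 lists outside-of-clinic self-administration separately from self-administration, which it defines as "Injections with PFS administered by the participant herself/himself or a caregiver either in clinic or outside of clinic".

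**When self-administration starts.** Protocol 6.7.2 offers the start at Visit 204 (Week 12), with in-clinic injections at Visits 204, 205 and 206. The study design figure legend likewise places the start in clinic at Week 12 and the move home at Week 24. Protocol 4.1 and 4.2 put the first outside-of-clinic dose at Visit 207 (Week 24).

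**The concern.** Two sets of instructions govern one endpoint in one analysis, and they disagree on who is counted and when the clock starts. Two programmers could each follow a section faithfully and report different subjects, 12 weeks apart, under the same label.

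The two results would answer different questions. Counted from Week 12, the result reflects injections given with staff assistance or under supervision. Counted from the first home dose, it reflects dosing at home, which is what the objective in 2.6 asks about.

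The populations also matter separately from the clock. At Visit 206 site staff judge whether the subject can dose at home, and Protocol 6.7.2 lets the subject, caregiver or investigator stop self-administration at any time. Study termination could also have stopped subjects between Visits 204 and 207. In-clinic-only self-injectors can therefore exist. They are in the 2.14.1 set but have no start date under the 2.6 clock. The SAP does not say whether they are left out or fall under the rule in 2.6.1 that scores missing data for this endpoint as non-response.

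**Working it through.** **Inputs.** Visit days from Protocol Table 8-1: Visit 204 = Day 85, 205 = Day 113, 206 = Day 141, 207 = Day 169, 208 = Day 197, 209 = Day 225, 210 = Day 253. Study weeks from SAP Table 2-1: Week x = Days 7(x − 1) + 1 to 7x. Twelve weeks = 84 days.

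**The plan's own figure.** In-clinic self-injections fall at Weeks 12, 16 and 20, four weeks apart. The next dose is at 12 + 3 × 4 = Week 24, Day 7 × 24 + 1 = 169. This agrees with the stated first outside-of-clinic dose at Visit 207.

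**Endpoint timing on the planned schedule.**

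| | Clock in 2.6 and Table 2-9 | Table 2-16 read from the in-clinic start |
|---|---|---|
| Time zero | Visit 207, Day 169 | Visit 204, Day 85 |
| Plus 12 weeks | 169 + 84 = Day 253 | 85 + 84 = Day 169 |
| UAS7 window | Week 36, Days 246-252 | Week 24, Days 162-168 |
| Self-injections in the 12 weeks before scoring | 3 at home (Days 169, 197, 225) | 3 in clinic (Days 85, 113, 141) |
| Scheduled home doses before scoring | 3 | 0 |

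The origins differ by 169 − 85 = 84 days. The Week 24 window closes on Day 168, the day before the first scheduled home dose.

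**Who could enter under Table 2-9.** The population label asks for one self-administration in TRT1B. SAP 2.1.1.2 defines that period as ("TRT1B): from Visit 204 to Visit 214 or 301, whichever comes first"). Because it opens at Visit 204, in-clinic injections at Visits 204-206 lie inside it, and the label alone does not exclude them.

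**The 2.14.1 set combined with the 2.6 clock.** Let p be the share of the set that self-injected only in clinic, and r the response proportion among those with a time zero. If the share p is kept and scored as non-response, the reported proportion is (1 − p) × r:

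- p = 5%: 0.95 r
- p = 10%: 0.90 r
- p = 20%: 0.80 r

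The documents give no value for p, so these are assumed. For illustration, with r = 55% (the planning rate at Week 12 in SAP 3.1, not a figure for this endpoint), the results are 52.25%, 49.5% and 44%.

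**The case against.** The strongest reply is that the protocol defines self-administration as dosing outside the clinic, in the glossary and again in section 4.2. On that definition the short phrase in Table 2-16 means the first home dose. SAP 2.14.4 sends the reader to 2.6 in any case, and Table 2-16 is only an overview of scope. Read this way, the clock is Week 36 throughout.

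That reading of the clock is reasonable, and it is why Week 24 is given only as a conditional result. It does not settle the matter. SAP 2.14.1 and Table 2-13 expressly count in-clinic injections, so the final-analysis set departs from the protocol's definition. The protocol's own section 6.7.2 and design figure also speak of starting in clinic at Week 12. Even if the home-dose clock is accepted, in-clinic-only subjects remain in the set without a start date.

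Several smaller points stand:

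- The endpoint text in SAP 2.6.1 and in Protocol 12.5.1 is also silent on setting. Only the 2.6 objective and the Table 2-9 time point name it.
- The population label in Table 2-9 can naturally be read as the 2.2.2 set.
- The wider set in 2.14.1 may have been chosen deliberately. If so, its time zero still has to be stated.
- The non-responder rule might be taken to cover subjects with no start date. The SAP does not say so, and that reading would count as failures people who never began home dosing.
- The analysis is descriptive, the study was terminated, and the unplanned interim tabulates UAS7 ≤ 6 by visit, including Weeks 24 and 36, for both sets. Those tables use observed data and are not anchored to each subject's start.

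**Conclusion.** The concern holds. The SAP gives conflicting rules for one listed secondary endpoint: the time point can be Week 36 or Week 24, and the set may or may not include subjects who never dosed at home. The 84-day difference assumes the planned visit schedule and the in-clinic reading of Table 2-16. The multipliers 0.95 to 0.80 assume that in-clinic-only subjects make up 5% to 20% of the set and are scored as non-responders. Neither the size nor the direction of the difference between the Week 24 and Week 36 results can be derived from the documents. No hypothesis test depends on this endpoint and the primary analysis is untouched, but the text should be corrected because the reported proportion cannot be interpreted without knowing which rule was used.

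**What to change.** In SAP 2.14.1 and Table 2-16, replace the self-administration set for this endpoint with the outside-of-clinic self-administration subpopulation of 2.2.2, and state that time zero is the first outside-of-clinic dose in TRT1B. Use the same population name in 2.6 and Table 2-9, so that subjects who self-injected only in clinic are plainly excluded. This matches the 2.6 clock and the protocol's definition. It also matches the starting point of the self-administration safety analysis in SAP 2.8.1.3, although that analysis has an additional majority-use rule for subjects who return to clinic dosing. If a result for in-clinic self-injection is wanted, report it separately under its own label and with its own time zero.

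The cost is SAP wording; no new imputation program is needed. The set becomes somewhat smaller. At an unchanged response rate the confidence interval widens by a factor of about 1/√(1 − p): 1.026, 1.054 or 1.118, that is about 2.6%, 5.4% or 11.8% wider for assumed p of 5%, 10% or 20%.

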2.14.2 Patient disposition, demographics, and other baseline characteristics

In the final analysis, patient disposition, demographics, medical history and other baseline data including disease characteristics will be analyzed as described in Section 2.3.

2.14.3 Treatments (study treatment, rescue medication, concomitant therapies, compliance)

In the final analysis, treatment exposure, and prior and concomitant therapies will be analyzed as described in Section 2.4.

2.14.4 Efficacy analyses at final analysis

Primary and some of the key secondary endpoints will be analyzed at the final analysis, as described in Section 2.5 and Section 2.6. [REDACTED]

2.14.5 Safety analyses at final analysis

[figure not shown]
In the final analysis, analyses for AEs will be conducted as described in Section 2.8.1 and 2.8.2.

Laboratory data will be analyzed as described in Section 2.8.4. Lab assessments will be summarized by visit for TRT1 for SAF. For the long term treatment subpopulation, summaries of clinical notable lab abnormality will be provided for TRT1+TRT2. For the long term treatment with a rest subpopulation, summaries of clinical notable lab abnormality will be provided for TRT1+OBS2+TRT2+FU.

ECG and cardiac imaging data will be analyzed as described in Section 2.8.5.1.

Vital signs will be analyzed as described in Section 2.8.5.2. Vital signs will be summarized by visit for TRT1 for SAF. For the long term treatment subpopulation and the long term treatment with a rest subpopulation, newly occurring or worsening vital signs outside notable ranges for the following parameters will be summarized for TRT1+TRT2, and TRT1+OBS2+TRT2+FU, respectively.

- Hypertension (systolic blood pressure of ≥ 140 mmHg and/or diastolic blood pressure of ≥ 90 mmHg).
- Hypotension (systolic blood pressure of < 90 mmHg and/or diastolic blood pressure of < 60 mmHg).
- Bradycardia (pulse rate below 60 bpm).
- Tachycardi (pulse rate above 100 bpm).

2.14.7 Biomarkers

In the final analysis, biomarkers analyses will be conducted as described in Section 2.11.

2.14.8 Handling of missing values/censoring/discontinuations

The missing data handling and imputation rules as described in Section 2.5.3 and Section 2.6.3 will be applied on the primary and some key secondary endpoints, respectively. All the other analyses in the final analysis will be based on the observed data.

Table 2-16 Overview of final analysis

Population/ Analysis /Study Period	Endpoints
First treatment period (TRT1)	
Analysis: Efficacy Populations: 1) FAS 2) Ligelizumab retreatment subpopulation 3) Ligelizumab responder retreatment subpopulation Period/time point: TRT1/up to week 52	
• Proportion of subjects with well-controlled urticaria ($UAS7 \leq 6$) at Week 12

Analysis: Efficacy
 
Populations:
 
 1) FAS 2) Ligelizumab retreatment subpopulation 
Period/time point: TRT1/up to week 52
	
 • Proportion of subjects with completely controlled disease (UAS7 = 0) at Week 12

Analysis: Efficacy
 
Populations:
 
 1) FAS 2) Ligelizumab retreatment subpopulation 
Period/time point: TRT1/up to week 52
	
 • Absolute and percent change from extension study baseline in the UAS7 and its components (ISS7 and HSS7) at Week 12 • Percentage of subjects achieving DLQI = 0-1 at Week 12

Analysis: Efficacy
 
Populations:
 
 1) FAS 2) Ligelizumab retreatment subpopulation 
Period/time point: TRT1A/up to week 12
	
 • Cumulative number of weeks that subjects achieve weekly angioedema activity score (AAS7) = 0 between extension study baseline and Week 12

Analysis: Efficacy
 
Population: Self-administration subpopulation
 
Period/time point: 12 weeks after starting self-administration in TRT1
	
 • The proportion of subjects with well-controlled disease (UAS7 ≤ 6), 12 weeks after starting self-administration


Analysis: Safety
 
Population: SAF
 
Period: TRT1A; TRT1B
	
 • TEAE, TESAE, TEAESI (crude incidence and EAIR) • TEAEs leading to discontinuation, death, (crude incidence and EAIR) • TEAE by severity (crude incidence) • Summary of vital signs, by visit • Summary of lab assessments, by visit

Entire treatment period (TRT1 + TRT2)
	

Analysis: Safety
 
Population:
 
1) Long term treatment subpopulation
 
Period: TRT1A; TRT1B; TRT2; TRT1+TRT2
	
 • TEAE, TESAE (crude incidence and EAIR), TEAESI (crude incidence and EAIR) • TEAEs leading to discontinuation (crude incidence and EAIR) • Summary of clinical notable lab abnormality (only TRT1+TRT2) • Summary of newly occurring or worsening vital signs (hypertension, hypotension, bradycardia, tachycardia; only TRT1+TRT2)

Analysis: Safety
 
Population:
 
1) Long term treatment with a rest subpopulation
 
Period: TRT1A; TRT1B; TRT2
	
 • TEAE, TESAE (crude incidence and EAIR) • TEAEs leading to discontinuation (crude incidence and EAIR) • AESI of CCV and malignancy (crude incidence and EAIR; only TRT1+OBS2+TRT2+FU) • Summary of clinical notable lab abnormality (only TRT1+OBS2+TRT2+FU)

	
 Summary of newly occurring or worsening vital signs (hypertension, hypotension, bradycardia, tachycardia; only TRT1+OBS2+TRT2+FU)
Entire study period (for the legal requirements of ClinicalTrials.gov and EudraCT)	
Analysis: Safety Population: SAF Period: Entire study	
 TEAE which are not serious adverse events with an incidence greater than 5% TESAE and SAE suspected to be related to study treatment

3 Sample size calculation

